## 10.4.4. Safety Analysis

The summary of safety results will be presented for Year 1, Year 2, and the combined Year 1 and Year 2 treatment periods.

Safety data including TEAEs and treatment emergent AESIs, vital signs, physical exams, laboratory tests, ECGs, and ADA formation will be listed and summarized by treatment group.

Thresholds for potentially clinically significant values (PCSVs) in laboratory parameters and vital signs will be defined by the sponsor and be in effect at the time of final SAP approval.

The time interval to detect any AEs, including AESIs (except JRs identified at the End of Study Phone Calls) is between the first dose of Year 1 study drug injection and the end of Follow-up Period, (either the week 72/Early Termination for those patients not proceeding into Year 2, the week 124E/Early Termination E for those patients proceeding into Year 2, or the Post-Op Joint Replacement Follow-up Visit 2), as well as study drug-related SAEs occurring between the end of Follow-up Period and the End of Study.

For safety variables, the following observation periods are defined:

- The Pretreatment Period is defined as the time from signing the ICF to before the first dose of study drug in Year 1.
- The Year 1 On-Treatment Period is defined as the day from first dose of Year 1 study drug through the day of last Year 1 dose + 4 weeks for those patients not proceeding

into Year 2, or up to the first dose of Year 2 study drug for those patients proceeding into Year 2. Summaries for the Year 1 On-Treatment Period will be based on the SAF – Year 1.

- The Year 1 Post-Treatment Period is defined from the end of the Year 1 On-Treatment Period to the Week 72/Early Termination Visit for those patients not proceeding into Year 2. Summaries for the Year 1 Post-Treatment Period will be based on the SAF Year 1.
- The Year 2 On-Treatment Period is defined as the day from first dose of Year 2 study drug through the day of last Year 2 study drug dose + 4 weeks for those patients proceeding into Year 2. Summaries for the Year 2 Post-Treatment Period will be based on the SAF Year 2.
- The Combined On-Treatment Period is defined as day from first dose of Year 1 study drug through the day of last SC dose + 4 weeks. Summaries for the Combined On-Treatment Period will be based on the SAF Year 1.
- The Year 2 Post-Treatment Period is defined from the end of the Year 2 On-Treatment Period to the Week 124E/Early Termination E Visit for those patients proceeding into Year 2. Summaries for the Year 2 Post-Treatment Period will be based on the SAF Year 2.

All safety analyses will be performed on Year 1 and Year 2 using the following common rules:

- The Year 1 baseline value is defined as the last available value before randomization.
- The Year 2 baseline value is defined as the last available value after the last dose of Year 1 treatment but before the first dose of Year 2 treatment.

#### 10.4.4.1. Adverse Events

## **Definitions**

The Year 1 and Year 2 TEAEs are defined as those that are not present at baseline or represent the exacerbation of a pre-existing condition during the respective on-treatment periods.

#### Analysis

All AEs reported in this study will be coded using the currently available version of the Medical Dictionary for Regulatory Activities (MedDRA®). Coding will be to lowest level terms. The verbatim text, the preferred term (PT), and the primary system organ class (SOC) will be listed. The focus of adverse event reporting in the clinical study report will be on TEAEs. Post-treatment AEs and all AEs during the study will be summarized similarly as TEAEs.

For the Year 1, Year 2, and Combined On-Treatment Periods, summaries of all TEAEs by treatment group will include:

- The number (n) and percentage (%) of patients with at least 1 TEAE by SOC and PT
- TEAEs by severity (according to the grading scale outlined in Section 9.5.1), presented by SOC and PT
- TEAEs by relationship to treatment (related, not related), presented by SOC and PT

• Treatment-emergent AESIs (defined with a PT or a pre-specified grouping)

Deaths and other SAEs will be listed and summarized by treatment group.

Treatment-emergent adverse events leading to permanent treatment discontinuation will be listed and summarized by treatment group similarly to TEAEs.

In addition, AESIs will be reported according to the adjudicated diagnosis. Imaging data related to AA including change from baseline in joint space width will be summarized.

## **10.4.4.2.** Other Safety

#### Vital Signs

Vital signs (temperature, pulse, blood pressure, and respiration rate) will be summarized by baseline and change from baseline to each scheduled assessment time with descriptive statistics for the Year 1, Year 2, the Combined On-Treatment Periods and the Post-treatment periods.

#### Laboratory Tests

Laboratory test results will be summarized by baseline and change from baseline to each scheduled assessment time with descriptive statistics for the Year 1, Year 2, the Combined On-Treatment Periods and the Post-treatment periods.

Potentially clinically significant value at any post-randomization time point will be summarized for each clinical laboratory test.

Shift tables based on baseline normal/abnormal and other tabular and graphical methods may be used to present the results for laboratory tests of interest.

Listings will be provided with flags indicating the out of laboratory range values.

## **10.4.4.3.** Treatment Exposure

Because of the half-life of the biologic being studied, the duration of SC study drug exposure for the Year 1 and Year 2 On-Treatment Periods will be presented by treatment group and calculated as:

= (Date of last SC injection of study drug in the respective on-treatment period – date of the first SC injection of study drug) +28

The number and percentage of patients exposed to SC study drug will be presented by specific time intervals for each treatment group for the Year 1 and Year 2 On-Treatment Periods respectively. The time intervals of interest will be specified in the SAP.

## 10.4.4.4. Treatment Compliance

Overall treatment compliance to SC study drug injection is defined as the actual number of SC injections compared to the expected number of SC injections during the on-treatment period up to treatment discontinuation, for the Year 1 and Year 2 On-Treatment Periods respectively. It is calculated according to the following formula:

 $\frac{\textit{Number of actual injections of study drug received during the treatment exposure period}}{\textit{Number of planned injections of study drug during the treatment exposure period on or}}} \ x \ 100$  before the time that the patient discontinued from the treatment phase of the study

The total number of actual doses of fasinumab will be summarized for the Year 1 and Year 2 On-Treatment Periods respectively.

Overall treatment compliance to oral study drug is defined as the total oral dose actually taken divided by the expected total oral dose of treatment during the treatment exposure period for Year 1 up to treatment discontinuation for Year 1. It is calculated according to the following formula:

```
\frac{\sum_{all\ treatment\ visits}(Number\ of\ pills\ dispensed-Number\ of\ pills\ returned)}{(date\ of\ last\ dose\ of\ oral\ study\ drug\ -\ date\ of\ first\ dose\ of\ oral\ study\ drug\ +\ 1)*2}\ x100
```

Since the oral study drug for Year 2 is naproxen prn, treatment compliance for oral study drug in Year 2 is not applicable and will not be summarized.

## 10.4.5. Analysis of Drug Concentration Data

Summaries of serum concentrations of functional fasinumab will be presented by nominal time point and dose. Plots of individual concentration over time will be presented by actual day (linear and log scales). Plots of mean or median concentrations of functional fasinumab will be presented by nominal day (linear and log scales).

No formal statistical analysis will be performed.

## 10.4.6. Analysis of Immunogenicity

Immunogenicity will be characterized by the ADA response observed:

- Pre-existing immunoreactivity, defined as a positive ADA assay response at baseline, with all post-dose ADA results negative, or a positive assay response at baseline, with all post-dose ADA assay responses less than 9-fold over baseline titer levels
- Treatment-emergent ADA response, defined as any post-dose positive ADA assay response when the baseline results are negative
- Treatment-boosted ADA response, defined as any post-dose positive ADA assay response that is 9-fold over baseline titer levels when baseline is positive in the ADA assay
- Maximum ADA Titer values
  - Low (titer < 1,000)
  - Moderate  $(1,000 \le \text{titer} \le 10,000)$
  - High (titer > 10,000)
- NAb status samples testing positive in the ADA assay will also be tested in the NAb assay and reported as positive or negative.

Listings of ADA positivity, ADA titers, and NAb positivity presented by patient, time point, and dose group will be provided. Incidence of treatment-emergent ADA will be assessed as absolute occurrence (N) and percent of patients (%), grouped by study cohorts and ADA titer level for each of the main 52-week treatment and long-term safety extension studies respectively.

The influence of ADAs on drug concentrations will be evaluated. Assessment of impact of ADAs on safety and efficacy may be provided.

# 10.5. Interim Analysis

The first-step analysis will consist of the primary and secondary efficacy analyses and will be conducted as soon as all patients have been randomized and all data for Year 1 (baseline through week 52) have been collected and validated. This will consist of the analyses of the primary and secondary efficacy endpoints at week 16 and/or week 44. Safety analysis will also be performed on the safety data for Year 1 and select safety data for Year 2.

No alpha adjustment is necessary, as the efficacy analyses for Year 1 will be the final primary and secondary efficacy analysis for efficacy and the efficacy analyses for Year 2 will only be descriptive and exploratory. The results of the analysis for Year 1 will not be used to change the conduct of the ongoing Year 2 period in any aspect.

Another analysis will be performed for regulatory purposes on the remaining Year 1 WOMAC and PRO assessments and safety data (collected during the Year 1 follow-up period) and any Year 2 efficacy and safety data available at the time of the data cut-off for interim analysis.

Additional analyses of other efficacy and safety data may be performed for regulatory purposes as needed.

As the primary and secondary efficacy analyses will have been completed in the first-step analysis, no adjustments due to multiplicity will be necessary for any subsequent analysis of the data.

Individuals unblinded to patient-level data for the first-step or any of the subsequent analyses will no longer be involved in the day-to-day conduct of the ongoing study. Patient-level results will not be released to any site-facing personnel or anyone who is directly involved in the conduct of the study.

# 10.6. Additional Statistical Data Handling Conventions

The following analysis and data conventions will be followed:

General rules for handling missing data:

- Rules for handling missing data for efficacy assessments due to missing individual item data will follow each questionnaire's instrument manual.
- If the start date of an AE or concomitant medication is incomplete or missing, it will be assumed to have occurred on or after the intake of study drug, except if an incomplete date (eg, month and year) clearly indicates that the event started prior to treatment. If the partial date indicates the same month or year of the intake of study drug date, then the start date by the study drug intake date will be imputed; otherwise, the missing day or month by the first day or the first month will be imputed.
- No imputations for missing laboratory data, ECG data, vital sign data, or physical examination data will be made.

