## 5. STATISTICAL METHODS

For continuous variables, descriptive statistics will include the following: the number of patients reflected in the calculation (n), mean, median, standard deviation, minimum & maximum and 1st & 3rd quartiles (Q1 & Q3).

For categorical or ordinal data, frequencies and percentages will be displayed for each category.

**Period of observation** – Unless otherwise stated, analysis of all safety variables captured at multiple visits will be analyzed by the following observations periods:

- The Pre-Treatment Period is defined as the time from signing the ICF to before the first dose of study drug in Year 1.
- The Year 1 On-Treatment Period is defined as the day from first dose of Year 1 study drug through the day of last Year 1 SC dose + 4 weeks for those patients not proceeding into Year 2, or up to the first dose of Year 2 study drug for those patients proceeding into Year 2. Summaries for the Year 1 On-Treatment Period will be based on the SAF – Year 1.
- The Year 1 Post-Treatment Period is defined from the end of the Year 1 On-Treatment Period to the Week 72/Early Termination Visit for those patients not proceeding into Year 2. Summaries for the Year 1 Post-Treatment Period will be based on the SAF – Year 1.
- The Year 2 On-Treatment Period is defined as the day from first dose of Year 2 study drug through the day of last Year 2 SC dose + 4 weeks for those patients proceeding into Year 2. Summaries for the Year 2 On-Treatment Period will be based on the SAF – Year 2.
- The Year 1 and 2 On-Treatment Period is defined as day from first dose of Year 1 study drug through the day of last SC dose + 4 weeks. Summaries for the Year 1 and 2 On-Treatment Period will be based on both the SAF – Year 1 and SAF-Year 2.
- The Year 2 Post-Treatment Period is defined from the end of the Year 2 On-Treatment Period to the Week 124E/Early Termination E Visit for those patients proceeding into Year 2. Summaries for the Year 2 Post-Treatment Period will be based on the SAF – Year 2.

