### **5.4. Prohibited Medications**

Summaries of prohibited medications will present patient counts (and percentages) for all prohibited medications, dictionary coded by WHO, by decreasing frequency of the overall group incidence (or fasinumab 1mg Q4W group incidence in tables where the overall is not presented) of ATC followed by ATC level 2, ATC level 4 and preferred term. In case of equal frequency across anatomic or therapeutic categories, alphabetical order will be used. Patients will be counted once in each ATC category (anatomic or therapeutic) linked to the medication but may be counted several times for the same medication. The following will be provided:

- All prohibited medications taken during the Pre-Treatment Period will be summarized by treatment group and overall, based on the SAF – Year 1 and SAF – Year 2 separately.
- All prohibited medications taken during the Year 1 Treatment and Follow-up Periods will be summarized by treatment group based on the SAF – Year 1. An analogous analysis will be performed for Year 2 Treatment and Follow-up Periods based on the SAF – Year 2.
- All prohibited NSAID medications taken during the Year 1 Treatment and Follow-up Periods will be summarized by treatment group based on the SAF – Year 1. An analogous analysis will be performed for Year 2 Treatment and Follow-up Periods based on the SAF – Year 2.

- The total number of days using prohibited NSAIDs during the Year 1 Treatment and Follow-up Periods (before AA for patients with AA) will be summarized by treatment group based on the SAF – Year 1. An analogous analysis will be performed for the Year 2 Treatment and Follow-up Periods based on the SAF – Year 2.
- The number of days from the last dose of study drug in Year 1 to the first NSAID dose will be summarized in the subset of patients in the SAF – Year 1 who do not continue into Year 2. Similarly, the number of days from the last dose of study drug in Year 2 to the first NSAID dose will be summarized based on the SAF – Year 2.

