### **Handling of Adverse Events or Concomitant Medications with missing or partial dates**

*Imputation of AE and Concomitant Missing and Partial start dates:*

Every effort will be made to collect the start dates of all AEs and concomitant medications. However, in the case the start date of an AE or concomitant medication is incomplete or missing, it will be assumed to have occurred on or after the first dose of study medication, except if an incomplete date (e.g., month and year) clearly indicates that the event started prior to treatment. If the partial date indicates the same month or year of the first dose of study medication date, then the start date of the first dose will be imputed, otherwise, the missing day or month by the first day or the first month will be imputed.

*Imputation of Partial AE and concomitant Medication Partial end dates:*

When only year is present, missing AE/concomitant medication end day and month will be imputed to the earlier of (study end date, 31DECYYYY).

When both month and year present, missing AE/concomitant medication end day will be imputed to the last day of the month.

There will be no attempt to impute completely missing AE or concomitant medication end dates. Events with an end date missing will be assumed to be ongoing at the time of data cut off.

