5.14	WOMAC patient assessment was not administered at Week 16 Primary Endpoint Analysis
8.04	Rescue medication administered during a protocol-prohibited period prior to scheduled visit during treatment period
8.05	Use of opioid medications anytime during treatment period
8.06	Use of non-protocol specified NSAIDs any time during the treatment
F.02	Confirmed treatment unblinding (in error)

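### Read as written, the partial start-date rule overwrites a known later month with the first-dose date, and it has no anchor at the end of treatment or at the first Year 2 dose

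*Protocol*

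**What the plan says.** Protocol 10.6 assumes that an incomplete or missing AE or concomitant-medication start falls on or after study drug intake, "except if an incomplete date (eg, month and year) clearly indicates that the event started prior to treatment". The intake date is imputed "If the partial date indicates the same month or year of the intake of study drug date". The fallback reads: "otherwise, the missing day or month by the first day or the first month will be imputed". SAP 6.4 repeats the rule, with the trigger worded "If the partial date indicates the same month or year of the first dose of study medication date". Its further rules on end dates and on a missing first-dose date do not change this.

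The start date decides the period. SAP 5 runs the Year 1 On-Treatment Period "through the day of last Year 1 SC dose + 4 weeks for those patients not proceeding into Year 2"; where a patient continues, that period closes when Year 2 dosing begins. SAP 5.8.1 separates treatment-emergent from post-treatment AEs, and SAP 4.3 separates concomitant from post-treatment medications, by those boundaries. SAP 5.4 also plans this summary: "The total number of days using prohibited NSAIDs during the Year 1 Treatment and Follow-up Periods (before AA for patients with AA"), and another of the days from last study drug dose in Year 1 to first NSAID dose.

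**The concern.** The year comparison is joined to the month comparison by a bare 'or'. A start with a known month, later in the calendar year of first dose, meets the trigger, so its month is replaced by Day 1.

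Patients who stop early are exposed to this. They include those who stop for AA, which requires permanent discontinuation (protocol 7.3.2.1) but not withdrawal: they are asked to keep attending visits (7.3.2, 9.6.1.1). Their post-treatment AEs can become Day 1 treatment-emergent AEs, and NSAIDs taken after AA can appear as NSAID use before it.

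The second gap is the anchor. The only date that the rule knows is the first dose of the study. Neither last SC dose + 4 weeks nor the first Year 2 dose enters it, although the summaries are divided at both.

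**Working it through.** The plan gives no figure for this rule, so there is none to reproduce.

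**Worked patient (illustrative dates).** First dose 15 Jan 2019. Last SC dose at the week 20 visit, day 141: 15 Jan + 140 days = 4 Jun 2019. On-treatment ends 4 Jun + 28 days = 2 Jul. AA on 15 Jun. NSAID start recorded as Aug 2019, stop 31 Aug. The NSAID prohibition lasts at least 16 weeks after the last SC injection (protocol 7.7.1): 4 Jun + 112 days = 24 Sep, so August lies inside it.

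| | Rule as written | Known month used |
|---|---|---|
| Imputed start | 15 Jan 2019 | 1 Aug 2019 |
| NSAID days to 31 Aug, inclusive | 229 | 31 |
| NSAID days before AA (15 Jan to 14 Jun) | 151 | 0 |
| Days, last SC dose to first NSAID | −140 | 58 |
| An AE with the same partial date | Day 1 TEAE | Post-treatment |

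The fourth row takes the last SC dose as the last study drug dose. A later last oral dose would make the first entry more negative.

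**How often the rule misplaces a partial date.** All 365 first-dose dates of a non-leap year were crossed with every true onset day in the stated range, equally weighted (an assumption; the documents give no enrolment calendar). Literal: a matching year triggers the first-dose date even when the month is known. Narrow: month and year are compared together when the month is known, and the year alone only when it is not. In both, a month match means the first-dose month of the first-dose year. The table gives the share wrongly placed in Year 1 On-Treatment.

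| Group and true onset | Month known, literal | Month known, narrow | Year only, either reading |
|---|---|---|---|
| Last SC dose week 16 (day 113), days 142–505 | 20.6% | 4.0% | 50.0% |
| Same, days 142–225 (NSAID prohibition) | 57.0% | 17.5% | 88.4% |
| Year 1 completer, days 366–505 | 10.5% | 10.5% | 80.7% |
| Year 2 AE, first Year 2 dose day 365 | 4.0% | 4.0% | 49.9% |

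Hand checks:
- Row 1, first-dose limb alone: onset day d falls in the first-dose year with probability (366 − d)/365. Summed over d = 142 to 365 this is (224 × 225/2)/365 = 69.04, and 69.04/364 = 19.0%. The other 1.6% comes from the fallback.
- Row 4, month known: a month of length L gives L(L − 1)/2 misplaced pairs. Seven months of 31 days, four of 30 and one of 28 give 3255 + 1740 + 378 = 5373, and 5373/365² = 4.0%.
- Row 4, year only: (365 × 364/2)/365² = 66,430/133,225 = 49.9%.

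**Which clause does it.** The first-dose limb drives the literal excess in rows 1 and 2. In row 3 it does nothing, because day 366 is never in the first-dose year. In row 4 it acts only when first dose was on 1 January (1–8 January if Year 2 starts on day 358). Rows 3 and 4 come from the fallback. Example: first dose 16 Jul 2018, first Year 2 dose 15 Jul 2019. An onset on 25 Jul 2019 recorded as Jul 2019 becomes 1 Jul (Year 1); a record of 2019 alone becomes 1 Jan (Year 1); Oct 2019 becomes 1 Oct and stays in Year 2.

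**The case against.** The narrow reading has a real case. The sentence can be read in parallel: compare the month when the day is missing, and the year when the month is missing. A wholly literal 'or' would also send Jan 2020 back to January 2019, which nobody can intend. A programmer may therefore code it narrowly, and the literal column would not arise. That stands, but the text does not say so, two programmers could differ, and the narrow reading leaves the year-only and Year 2 figures unchanged.

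Defaulting to treatment-emergent is a deliberate conservative convention, like counting missing severity as severe, and it applies to all arms. It suits unknown timing. It does not justify discarding a known month, and it is not conservative for Year 2 AEs, which it undercounts in Year 2. The combined Year 1 and 2 summaries do keep those events.

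Four stronger inferences are not supported:
- That every partial date is moved. Starts clearly before treatment are exempt, and about 96% of Year 2 AEs and 89% of completers' post-treatment events with a known month stay in the right period.
- That patients would be wrongly dropped from the per-protocol set under the SAP 10.4 deviation "Use of non-protocol specified NSAIDs any time during the treatment". SAP 4.4 has the study team review the medication list and record deviations; nothing derives them from imputed dates.
- That joint damage would be attributed to NSAIDs. The SAP 5.4 table is descriptive, and no planned analysis models AA on NSAID days.
- That any late NSAID start inflates the prohibited-use count. In the worked patient an October start would fall after 24 September, the end of the minimum 16 weeks, so it may not be a prohibited use at all.

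**Conclusion.** The point holds as a defect of wording and of anchoring. Followed literally, the rule overrides a known later month in the first-dose year, and this reaches essentially only patients who stop early: with last dose at week 16, 20.6% of post-treatment onsets with a known month are misplaced, against 4.0% on the narrow reading. Independently of the reading, the missing Year 2 anchor sends about 4% (month known) or 50% (year only) of partially dated Year 2 AEs into Year 1.

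These percentages describe the rule under uniform dates. They do not predict how many records are affected, because the frequency of partial dates is not stated. Year-only starts should be uncommon with visits every 4 weeks. What is touched is descriptive: TEAE and post-treatment AE tables, concomitant-medication tables and the NSAID summaries. No efficacy test changes. The text should be corrected because period assignment depends on it and the correction is cheap.

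**What to change.** In protocol 10.6 and SAP 6.4, keeping the exemption for starts clearly before treatment:

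1. Month and year known: impute the first-dose date only if both match the first dose; otherwise the first day of the known month.
2. Only the year known: impute the first-dose date if the year matches; otherwise 1 January.
3. In either case, if the item was first recorded after Year 2 entry and was absent at earlier visits, do not impute a start before the first Year 2 dose.
4. Likewise, if it was first recorded after last SC dose + 4 weeks and was absent at earlier visits, use the known month or the visit of first recording, so that it is not placed on-treatment by default.

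Items 1 and 2 alone leave the year-only and fallback errors in place; items 3 and 4 address them. The cost is a short text change and some programming. No new data are needed, but the imputation code must use the visit at which each item was first recorded.
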